Title: Stand if You Can: A Standing Intervention in Long Term Care

NCT Number: NCT03796039.

Version Date: May 1 2020

METHODS

Study Setting

The *Stand if You Can* trial is a multi-center, parallel group, RCT using intention-to-treat analysis. For pragmatic reasons, this trial is a single blinded study. It will take place in four different LTC facilities within two cities in the Province of New Brunswick, Canada. Two of the selected facilities will be in each city. Each facility is designated by the Province of New Brunswick as a level three LTC facility (1). This means that the clients have health limitations which require assistance and supervision on a 24-hour basis (1,2). Three of the four facilities are sister nursing homes, meaning they follow the same policies, similar procedures, and have identical floor plans. Registered nurses, licenced practical nurses and rehabilitation assistants are regular staff at all the participating homes. Each of the chosen LTC facilities have the space and resources necessary to assist in the operation and delivery of the trial.

Participant timeline

All of the outcome variables, and participant characteristics will be collected at pre (T1) and post (T2) testing. Data regarding fall information will have two additional data collection time points, including 6 months prior to the intervention (-T) and 6 months follow-up (T3). Attendance will be collected during the intervention, between T1 and T2. See Figure 1 for timeline.

Eligibility Criteria

Inclusion criteria:

- 1) Participants must be a resident of one of the four participating LTC facilities at the time of recruitment.

- 2) Participants must be able to provide consent or have Substitute Decision Maker agree on their behalf to participate in the study if required.
- 3) Participants must be able to walk for 10 meters, with or without a walking aid.

Exclusion Criteria:

- 1) Residents identified by the LTC facility's rehabilitation staff as being too high risk for falling, or unable to participate for safety reasons.

Interventions

Social Standing Intervention

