Participants residing in one of the facilities randomized to the intervention will be offered up to 100 minutes of supervised standing per week, for 22 weeks. To achieve 100 minutes of standing each week, participants will stand (either on their own or with a group of their peers) for ten minutes at a time, twice per day, five days per week (Monday-Friday). Participants will be allowed up to five breaks per session of undefined length to assist in attaining the objective of 100 minutes of standing per week. During the standing time research assistants (RA) will engage socially with the participants, with a 1:4 ratio of RA and participants. If the LTC facility is hosting a stationary group activity during the standing time participants will be allowed to partake, provided they can do so while standing. If a participant is able, they will be allowed to stand for 20 consecutive minutes by week 11 and onward, as opposed to two separates 10-minute sessions. The opportunity to have two separate sessions will still be an option for those who do not wish to stand for 20 minutes in one session. A session will be terminated if the maximum time is reached, if the participant takes all five permitted breaks, or if the participant requests to stop or shows signs of physiological distress. Participants will be encouraged to stand five days each week. However, if the participant displays strong verbal disinterest, refuses participation, is

non-compliant, or is physically unable to attend, they will be allowed to miss the planned session. Participants will not be excluded from the study or subsequent analyses due to non-compliance to the intervention. Following a request from a consenting participant, LTC facility staff, or the Substitute Decision Maker will a participant no longer be asked to participate in the standing sessions. Adherence to the intervention will be monitored and tracked using a daily log. Participant attendance, total standing time, number of breaks taken, and total group size (if applicable) will be recorded at each session. These logs will be kept at the local research institution and brought to the LTC facility by RAs each day.

Social Exposure (control)

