Metabolic profile will be assessed as participant high-density lipoprotein, low-density lipoprotein, total cholesterol, triglyceride, and blood glucose using a CardioChek Professional Analyzer system (PTS Diagnostics, Whitestown, Indiana, USA). Following a finger prick conducted using a single use lancet, approximately 60 μ L of whole blood will be collected. Forty μ L will be used to assess blood lipids via a Lipid Panel (PTS Diagnostics, Whitestown, Indiana, USA), with the remaining 20 μ L used to assess blood glucose via a Glucose Panel (PTS Diagnostics, Whitestown, Indiana, USA).

Cognition will be assessed using the Mini-Mental State Examination (MMSE) questionnaire(6). Participants who score 18 or above will be asked to complete subsequent questionnaires pertaining to their psychosocial health. These questionnaires include the Geriatric Anxiety Inventory(7), Falls Efficacy Scale – International (FES-I) (8), Geriatric Depression Scale Short Form (9), the DeJong Loneliness Scale (10) and the UCLA Loneliness Scale (11).

Falls, injuries due to falls, and hospitalization will be collected from the participants accident report provided by the LTC facility. At 6 months follow-up, data will be collected retrospectively from 6 months prior to the intervention and up until the 6-month follow up. This data includes the number of falls, type and number of injuries as well as the number of hospital visits.

Attendance will be collected throughout the intervention. The daily total standing time, number of breaks, the use of an assistive device as well as the group size will be recorded.

Sample Size

Sample size was estimated based on anticipated changes in gait speed, the primary outcome of this trial. The minimum clinically important difference in gait speed is 0.1 m/sec

(18). With a cluster size of two, and assuming a small-to-moderate clustering effect (intraclass correlation coefficient = 0.075), within-group standard deviation of 0.10 m/s, and alpha = 0.05, recruiting 36 participants per group will provide 80% power to detect a clinically important change in gait speed. To account for an expected loss to follow-up of 20%, we plan to recruit 44 participants per group (total n=88).

Recruitment

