As this is an intention to treat trial, all data will be evaluated based on the randomized group allocation. Generalized linear models – specifically an ANOVA analysis, will be used to compare the dependant variable (gait speed) between intervention groups while accounting for potential confounders (e.g., age, sedentary level). Secondary outcomes such as sedentary behaviour, leg strength, sit to stand ability, balance performance, psychosocial outcomes, and blood lipids and blood glucose will each be analyzed with separate linear models as well, in relation to intervention group. Consistent with an intention-to-treat approach, the models will estimate missing values. When possible, general linear models will also be used to evaluate subgroup analyses, where health conditions will be considered a fixed variable in relation to gait speed performance.

1. Standards Manual: Nursing Home Services. Department of Social Development, Government of New Brunswick; 2019.
2. Banjeer A. An Overview of Long-Term Care in Canada and Selected Provinces and Territories. Place Call Home Long Term Care Can. 2009;29–57.
5. C. X. Yang. Low-Cost Experimental System for Center of Mass and Center of Pressure Measurement (June 2018). IEEE Access. 2018;6:45021–33.
10. De Jong Gierveld J, Van Tilburg T. The De Jong Gierveld short scales for emotional and social loneliness: tested on data from 7 countries in the UN generations and gender surveys. Eur J Ageing. 2010/04/09 ed. 2010 Jun;7(2):121–30.

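### Falls, injuries and hospital visits have no named analysis, and the only secondary model offered is linear without person-time, so a difference between arms in time at risk could be read as a difference in falls

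*Combined protocol and SAP*

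**What the plan says.** The Secondary Outcomes section states: "Falls, injuries due to falls, and hospitalization will be collected from the participants accident report provided by the LTC facility". These are counts: "This data includes the number of falls, type and number of injuries as well as the number of hospital visits". They span three windows, since "data will be collected retrospectively from 6 months prior to the intervention and up until the 6-month follow up", and the Interventions section sets the middle window by offering "up to 100 minutes of supervised standing per week, for 22 weeks". Under Participant timeline, fall information is the only outcome given collection points before T1 and after T2.

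The Statistical Analysis section uses ANOVA for gait speed and then says that the other outcomes "will each be analyzed with separate linear models as well, in relation to intervention group". It identifies those outcomes by examples: "Secondary outcomes such as sedentary behaviour, leg strength, sit to stand ability, balance performance, psychosocial outcomes, and blood lipids and blood glucose". Falls, injuries and hospital visits are not among the examples. The section gives no count distribution, rate, offset or person-time, and does not say which fall window is compared. It says that the models will estimate missing values, without naming a method and without saying how a partly observed period is treated.

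Two other places bear on time at risk. The residence criterion under Eligibility Criteria is only that "Participants must be a resident of one of the four participating LTC facilities at the time of recruitment", with no minimum stay. The Sample Size section expects 20% loss to follow-up, not split by arm, in the calculation for gait speed.

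**The concern.** A count depends on how long the person was watched. A resident who dies or moves out in week 10 can have no further falls recorded by the facility. In a linear model of counts, that resident looks like someone who fell little. If one arm loses more residents, or loses them earlier, its mean count drops although its fall rate is unchanged.

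Allocation makes this plausible. The Interventions section speaks of facilities being randomised, and the Allocation section specifies cluster randomisation 1:1. With four facilities, that is two per arm. Study Setting says that only three of the four are sister homes. Randomising four units cannot be relied on to balance death, discharge or recency of admission, so one facility's turnover can become a difference between arms.

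At stake is whether a standing programme appears to lower, raise or leave unchanged the number of falls in residents who need round-the-clock assistance. Skewness of the counts is a lesser issue. Person-time is the main one.

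**Working it through.** **The plan's own figures.** The documents give no rate, dispersion or power for falls, so there is no fall figure to reproduce. The 20% loss appears only where 36 per group becomes 44 (36 × 1.20 = 43.2, rounded up). It concerns gait speed, which needs a walk test in person at T2.

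**Inputs from the documents.** Intervention 22 weeks; follow-up 6 months, taken as 26 weeks; 44 recruited per arm.

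**Assumptions.** The true fall rate is the same in both arms. A fraction *d* of an arm dies or leaves at times spread uniformly over the period after baseline. Average loss across arms is 20%. Fall rates of 1 to 3 per person-year are used for scale.

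**Formula.** Time after baseline is T = (22 + 26)/52 = 0.923 years. A lost resident contributes half of T on average, so the expected raw count per recruited resident is rate × T × (1 − d/2). With equal rates, the ratio of arm B to arm A is (1 − d_B/2)/(1 − d_A/2).

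| Loss A / B | Exposure A | Exposure B | Ratio B/A | Shortfall in B, falls per person at 1 to 3 per year |
|---|---|---|---|---|
| 20% / 20% | 0.900 | 0.900 | 1.00 | 0 |
| 15% / 25% | 0.925 | 0.875 | 0.946 | 0.05 to 0.14 |
| 10% / 30% | 0.950 | 0.850 | 0.895 | 0.09 to 0.28 |
| 0% / 40% | 1.000 | 0.800 | 0.80 | 0.18 to 0.55 |

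With log person-time as offset, the model is for count divided by time, and the expected rate ratio is 1.00 in every row, provided that leaving is unrelated to falling.

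**Effect on the test.** A simulation with no true effect used 2,000 runs, 44 per arm, 2 falls per year, overdispersed counts (dispersion 1) and no clustering. It compared a t-test on raw counts with a Poisson log-link model with offset and robust standard errors.

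| Loss A / B | False positives, raw counts | False positives, with offset |
|---|---|---|
| 20% / 20% | 5.0% | 5.8% |
| 10% / 30% | 5.8% | 5.9% |
| 0% / 40% | 12.2% | 6.0% |

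Simulation error is about √(0.05 × 0.95/2000) = 0.5 percentage points. At this sample size a moderate imbalance shifts the estimate but barely moves the test; only the extreme split does.

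**The case against.** The strongest reply is that the plan is silent rather than wrong. A reader might infer that it assigns falls to a linear model on raw counts. It does not: falls are not on the list, the list is open, and nothing says that unadjusted values are analysed. That stands. What remains is that linear models are the only ones offered for secondary outcomes, so they are the natural default for anyone following the text.

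A reader might also infer that bias is certain. It is not. The windows are the same in both arms, and equal loss gives a ratio of 1.00. Two related figures should not be used as measures of error here. A 22-week window holds about 16% fewer falls than 6 months (22/26.09 = 0.843), and a resident admitted two months before the start shows a third of a 6-month count. Both concern comparisons between periods. The text plans a comparison between groups and no before-after contrast.

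Nor is 20% a forecast of lost fall data. Fall records come from the facility, and residents who stop attending stay in the analyses, so someone who misses the walk test may have complete fall records. Only death or departure shortens exposure, and no figure is given for either.

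The statement that models will estimate missing values might be offered as an answer. It is not one: a shortened count is an observed low number unless the plan says that it is to be treated as incomplete.

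Finally, the documents do not call falls the main harm signal, and residents judged too high risk for falling are excluded. That limits how much weight the point can carry, but does not remove it.

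**Conclusion.** The point holds in a limited form and should be addressed before analysis. Three secondary count outcomes have no named analysis, and the one secondary model on offer ignores time at risk. If that model is used, imbalance in time at risk could produce a spurious difference: none with equal loss, about 5% at 15% versus 25%, about 11% at 10% versus 30%, and 20% at 0% versus 40%. These splits, the uniform timing and the 20% average are assumptions made for scale, and the documents neither support nor exclude any of them. For moderate splits the harm is to the estimate rather than to the false-positive rate. The documents do not support a statement that the planned analysis will misread falls. They support the statement that it could, and that nothing written prevents it. No sample-size figure is affected.

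**What to change.** Add to the Statistical Analysis section a separate paragraph for falls, injuries due to falls and hospital visits:

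- A negative binomial (or quasi-Poisson) model by randomised arm, with log days in residence in the window as offset.
- The pre-period rate as covariate, with pre-period days taken from length of stay, which is already collected, and capped at 6 months.
- Rate ratios with confidence intervals, reported separately for the 22-week intervention and the 6-month follow-up.
- An explicit method for facility clustering. The section states no facility term for any outcome, so there is none to carry over from gait speed. With four facilities in two arms, only 4 − 2 = 2 degrees of freedom remain between facilities, and the plan should acknowledge this limit.
- A table of days in residence, deaths and departures by arm and facility.

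The cost is a paragraph of text and the extraction of admission, death and discharge dates from facility records that the study already uses. One limit remains: the offset corrects for the length of observation, not for departure that is itself related to falling, such as transfer or death after a fall. The tabulated reasons for leaving would show how far that matters.

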Participants residing in the control facilities will spend 20 consecutive minutes engaging in social activities with the RA. Social activities will be structured similarly to the intervention group. Some examples include sharing jokes and stories, playing charades, and signing along to music. Social activities will be completed in groups or individually, with participants allowed to join the activity by whatever means of transportation they chose. There will be no limit to the number of participants allowed to attend each group social activity session, with the number of staff ranging from one to two. Adherence to the social activity will be monitored and tracked using a daily log noting attendance, total group size (if applicable), the length of the activity. These logs will be kept at the local research institution and brought to the LTC facility by RAs each day.

Variables and Measures

Participant Characteristics

Participant age, sex, height, weight, medical condition, length of stay in the LTC facility, transfer status, and frailty status will be collected from LTC staff at pre-testing (T1) and post-testing (T2) using the most recent data from participants' LTC health records.

Primary outcome

The primary outcome of this study is gait speed. To measure gait speed, participants will perform a 10-meter walk at pre and post testing, with the first and last two meters used as acceleration and deceleration zones. Gait speed will be measured over the intermediate 6 meters. If required, participants will be permitted to use an assistive device while closely monitored by RA with an available wheelchair made available for safety. Participants will be instructed to walk at a comfortable speed and to start walking when signalled. Using a stopwatch, a RA will manually start timing the participant once the participant's foot or walking aids crosses the 2-meter mark, whichever occurs first. The timer will be stopped once the participant or the walking aid reaches the 8-meter mark and the total time will be recorded in seconds. Once a participant completes the first trial, the participants will take a brief pause and a second trial will be completed. The average of the two values will be used for analysis.

Secondary Outcomes

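### The plan says its models will estimate missing values but names only an ANOVA for gait speed, and T1 gait speed is not listed as a covariate

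*Combined protocol and SAP*

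**What the plan says.** Under Statistical Analysis, a generalized linear model is announced, "specifically an ANOVA analysis, will be used to compare the dependant variable (gait speed) between intervention groups". Adjustment is described as "accounting for potential confounders (e.g., age, sedentary level", an open list that does not mention T1 gait speed. The secondary outcomes get separate linear models. The section then states "Consistent with an intention-to-treat approach, the models will estimate missing values". No imputation method, likelihood-based model, missing-data assumption or sensitivity analysis is named anywhere in the document.

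T1 gait speed will be available. Participant timeline says "All of the outcome variables, and participant characteristics will be collected at pre (T1) and post (T2) testing", and Primary outcome says "To measure gait speed, participants will perform a 10-meter walk at pre and post testing". Each resident therefore has at most one post-baseline value of the primary outcome.

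Sample Size says "Sample size was estimated based on anticipated changes in gait speed, the primary outcome of this trial", and anticipates missing data: "To account for an expected loss to follow-up of 20%, we plan to recruit 44 participants per group (total n=88"). Under Interventions, "Participants will not be excluded from the study or subsequent analyses due to non-compliance to the intervention".

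**The concern.** The promise and the named method do not match. An ordinary ANOVA drops a resident whose outcome is missing, and a classical repeated-measures ANOVA drops a resident with no T2 value. A likelihood-fitted model of T1 and T2 would keep those residents, but the text does not name one. Nor does it say whether the dependent variable is the T2 value, the change, or both time points.

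Two things are at stake. The first is precision: T1 gait speed is the obvious predictor of T2 gait speed, and leaving it out wastes information already collected. The second is bias: if slower walkers are lost more often and loss differs by arm, the candidate analyses give different answers, and the analyst could choose among them after seeing the data. Keeping non-compliant residents in the study limits loss but cannot secure a T2 walk from someone who has died, left or can no longer walk.

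**Working it through.** **Inputs from the plan (Sample Size).** Difference 0.1 m/s, SD 0.10 m/s, ICC 0.075, alpha 0.05, power 80%, 36 per group, 20% loss, 44 per group recruited.

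**Inputs assumed here, not in the plan.** Loss of 25% in one arm and 15% in the other; T1-T2 correlation 0.7; equal SDs at T1 and T2; no true effect. Graded loss means that the odds of loss double or triple per SD slower.

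**1. The plan's own figure.** Unclustered n = 2 × (0.10 × (1.960 + 0.842)/0.1)² = 15.70 per group. With two facilities per arm and 18 residents each, the design effect is 1 + 17 × 0.075 = 2.275, and 15.70 × 2.275 = 35.7, so 36. Then 36 × 1.20 = 43.2, so 44. (Dividing by 0.80 gives 45.)

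**2. Residents at stake.** 0.20 × 88 = 17.6, about 18 without a T2 walk; 0.80 × 44 = 35.2 per group remain. By the plan's formula, power is 79.95% at 35.2 per group and 80.3% at 36. Dropping these residents hardly touches planned power.

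**3. Standard error.** With 35 per arm, 17.5 per facility: design effect 1 + 16.5 × 0.075 = 2.24; SE = 0.10 × √(2/35) × √2.24 = 0.036 m/s.

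**4. Precision.** Adjusting for T1 multiplies the individual-level residual variance by 1 − correlation²: 0.75 at 0.5, 0.51 at 0.7, 0.36 at 0.8. At 0.7 with the ICC unchanged, the SE becomes 0.036 × √0.51 = 0.026 m/s.

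**5. Bias.** Selective loss raises the mean of the driving variable among completers by the following amounts.

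| Odds of loss per SD slower | 15% loss | 25% loss | Difference (m/s) |
|---|---|---|---|
| ×2 | 0.0098 | 0.0160 | 0.0062 |
| ×3 | 0.0142 | 0.0228 | 0.0086 |

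If loss follows T2, that difference is the bias of an ANOVA of T2 values. If loss follows T1, the bias is 0.7 times it: 0.0043 and 0.0060. Simulation with 2,000,000 records agrees and gives the other analyses (m/s; a positive value favours the arm with more loss):

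| Loss driven by | Odds | T2 ANOVA | Change score | T1-adjusted |
|---|---|---|---|---|
| T1 | ×2 | 0.0042 | −0.0018 | 0.0000 |
| T1 | ×3 | 0.0057 | −0.0025 | 0.0000 |
| T2 | ×2 | 0.0061 | 0.0017 | 0.0032 |
| T2 | ×3 | 0.0086 | 0.0027 | 0.0047 |

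Against the SE, 0.0043/0.036 = 0.12 and 0.0086/0.036 = 0.24. With 20% loss in both arms and one mechanism, every bias is within 0.0004 of zero. In the extreme case where all those lost are the slowest, the T2 ANOVA bias is about 0.010 (T1-driven) or 0.015 (T2-driven), or 0.3-0.4 SE.

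**6. Dependence on the correlation.** Under graded T2-driven loss, T1 adjustment leaves about 0.5 of the T2 ANOVA bias at correlation 0.7 (0.0032/0.0061 = 0.52; 0.0047/0.0086 = 0.55), about 0.4 at 0.8 and about 0.2 at 0.9.

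**7. Meaning of the SD.** The plan does not say whether 0.10 m/s is the SD of T2 values or of change. If it is of change, the SD of T2 at correlation 0.7 is 0.10/√(2 × 0.3) = 0.129, and the bias figures and the SE both scale by 1.29.

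**The case against.** The wording is ambiguous rather than contradictory. The section speaks of generalized linear models, an ANOVA and linear models, and the sample size is framed in terms of change. A repeated-measures model fitted by likelihood would use every resident and could honour the missing-values sentence. The covariate list is open, so T1 gait speed could be added. This stands: a reader might infer that the plan excludes T1 adjustment, or that the analysis must be complete-case, and the text supports neither.

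The harm is also small and rests on invented inputs. The loss rates, the correlation and the odds are not in the documents; with graded loss the T2 ANOVA bias is under a tenth of the 0.1 m/s target, and with change scores it is smaller still. This stands too. A reader might infer that the trial will be biased or underpowered on this account. The documents do not show loss that differs by arm, and the sample size already allows for 20% loss.

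Finally, T1 adjustment is not uniformly better. If loss is driven by T2 itself, change scores are biased less in the table above. That is correct, and is the reason for the sensitivity analysis. What the objection does not remove is that the plan makes a promise about missing data without naming any method that keeps it, and leaves its best available covariate unstated.

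**Conclusion.** The point holds as a gap in specification with a nearly free improvement, and should be corrected. That the only method named does not, in its ordinary form, estimate missing values, and that T1 gait speed is not listed, can be read directly from the text and depends on no assumed figure.

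The gain in precision depends on a T1-T2 correlation that the plan does not give. The bias figures are an illustration, not a forecast: 0.1-0.2 SE with graded, arm-dependent loss, and about zero if the pattern of loss is common to both arms. When loss depends on T1, an ANOVA of T2 values and an analysis of change are biased in opposite directions, so the unstated choice can move the estimate either way.

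**What to change.** - **Primary analysis.** Replace the ANOVA sentence for gait speed with one analysis: T2 gait speed on arm, with T1 gait speed as a covariate, keeping age and sedentary level (measured at T1). The equivalent likelihood model of T1 and T2 with a common T1 mean is an alternative. The regression also uses only residents with a T2 walk; its gain is the T1 adjustment, not the number kept.
- **Missing data, all outcomes.** Replace the missing-values sentence rather than deleting it, because it is the only such provision for the secondary outcomes. State that each secondary outcome measured at T1 and T2 is adjusted for its own T1 value or fitted by the same likelihood model, and that this is valid under missing-at-random given T1 and the covariates. Do not claim that an ANOVA estimates missing values.
- **Reporting.** Give T2 losses and reasons by arm, with deaths and residents unable to walk shown separately. Impute no walking speed for deaths.
- **Sensitivity analysis.** Impute missing T2 gait speeds, then shift them by 0 to −0.10 m/s in each arm separately and in both. At 20% loss the largest one-arm shift moves the contrast by 0.20 × 0.10 = 0.02 m/s: about 0.6 of the unadjusted SE (0.02/0.036), or about 0.8 of the T1-adjusted SE (0.02/0.026, at correlation 0.7 and unchanged ICC).
- **Clustering.** How the model handles facility is a separate point and is not settled by this change.

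Cost: two sentences rewritten, a little more analysis, and a log of the reason for each missing T2 value, which the plan does not mention. No new measurement is needed. Missing-at-random remains untestable; if loss is driven by T2 itself, T1 adjustment removes only part of the bias, by an amount that depends on the unknown correlation, and change scores would then be biased less.
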